Bone Marrow Aspirate Concentration in Posterior Cervical Fusion

Specific Aim:

1) Measure the rate of bony fusion in high-risk patients undergoing posterior cervical decompression and fusion.

Hypothesis: Bone marrow aspirate concentration combined with locally harvested autograft results in equivalent rates of bony fusion, as compared to current best practice in high-risk patients undergoing posterior cervical decompression and fusion.

Outcome Measures

Primary Outcome Measures: Rate of fusion – (6, 12, and 24 months) *Rate of fusion will be assessed by flexion extension X-rays at routine follow-up, translation method (<2mm) and/or by computed tomography (CT) scan at 2 year post-operatively.*

Secondary Outcome Measures: Short Form 36 (SF-36), Neck Disability Index (NDI), Myelopathy Disability Index (MDI), and modified Japanese Orthopedic Association score (mJOA) (pre-operative, 3 months, 6 months, 12 months, and 24 months), rates of intraoperative and post-operative complications, and rates of reoperation.

Significance and Biological Relevance: Spine surgery has increased substantially in the U.S. during the past decade, with an estimated 100,000 patients undergoing cervical procedures annually.¹ As the demographics of an aging population begin to increase their utilization of healthcare resources, surgeons will undoubtedly be faced with an increasing number of high-risk patients. Osteoporosis, rheumatoid arthritis, smoking, and obesity have all been shown to be significant risk factors for surgical complications following spinal arthrodesis.^{3,5,6} Nicotine has a direct inhibitory effect on autologous cancellous bone graft revascularization, significantly increasing the rate of bony non-union.^{3,18} Similarly, obesity has been demonstrated to represent a significant risk factor for subsequent pseudoarthrosis and has been linked to nearly a 100% higher in-hospital complication rate.^{10,11}

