Bone marrow aspirate (BMA) concentration represents a potential osteoinductive alternative to rhBMP.² BMA can be easily obtained with a needle or through a minimal incision and it contains hematopoietic cells and mesenchymal stem cells (MSC).¹² BMA can be used immediately during the operation, usually in combination with a carrier such as cadaveric allograft or demineralized bone matrix, or can be subjected to further processing to concentrate MSCs, platelet-rich plasma, or CD34+ cells. MSCs exhibit potency to differentiate into mesenchymal tissues, including bone, cartilage, muscle and adipose tissue.⁴ Multiple authors have reported good clinical outcomes with difficult osseous non-unions^{8,9,17} of the extremities or jaw, yet the quality of evidence supporting the efficacy of BMA concentration during surgical management of degenerative spine disease remains limited.^{2,13} With the recent shift in medicine towards a value-based system, demonstration of cost-effectiveness in tandem with clinical efficacy is of paramount importance. The results of this study will provide not only benchmark data for further modeling an incremental cost-effectiveness ratio, but more importantly determine whether bone marrow aspirate concentration can reliably improve bony fusion in a high risk patient population undergoing posterior cervical arthrodesis.

Approach: A prospective single institution non-blinded randomized trial. Patients with symptomatic cervical myelopathy or radiculopathy amenable to management with a posterior cervical decompression and fusion will be recruited to enroll in the study in either the outpatient or inpatient setting by an orthopaedic or neurosurgery physician. As part of standard

of care pre-operative work-up patients will undergo cervical MRI and or cervical CT myelogram with plain cervical X-rays, in addition to a detailed physical examination, demographic data and outcomes questionnaires, including the Neck Disability Index (NDI), Short Form 36 (SF-36), (Myelopathy disability index (MDI), and modified Japanese Orthopedic Association (mJOA) score). These outcomes measure sensibility, motor strength, bladder function and one's ability to perform specific tasks such as rising from a chair, performing fine-motor tasks and personal hygiene practices. All pre-operative imaging again is done as part of the standard of care and often times is done prior to patient referral for surgical consultation

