Inclusion criteria will include cervical alignment allowing management with a posterior approach. Post-operative X-rays scans will be obtained at the 6-week, 12 week, 6-month, 12 –month and 24 month time points as part of the standard post-operative assessment. Detailed physical exams and patient reported questionnaires (NDI, SF-36, MDI, mJOA) will be obtained at these follow-up points.

100 consecutive high-risk patients who meet the following inclusion criteria: are 18-75 years of age, require a cervical spine MRI as part of their standard of care show evidence of CSM, and have cervical alignment allowing posterior instrumented fusion. High-risk will be defined as having a diagnosis of rheumatoid arthritis, osteoporosis, current smoker, or BMI >30. Patients will be excluded if they have any MRI incompatible devices, have any prior cervical instrumentation, require an instrumented anterior cervical fusion, or have an underlying neurological condition affecting the cervical spine (MS, ALS, HIV).

Patients will be sequentially randomized to one of two treatment groups. Group I, will receive current best practice for posterior instrumented fusion (locally harvested autograft, demineralized bone matrix, and cadaveric allograft). Group II, will receive locally harvested autograft and 20 cc of bone marrow aspirate concentration. To assist with analysis, we will collect information from patients' hematology results, obtained per their standard of care pre-operative workup. All patients will be treated post-operatively at the discretion of the treating surgeon. All patients will follow-up at 6 weeks, 3 months, 6 months, 12 months, and 24 months. At the 6, 12, and 24-month follow-up all patients will undergo flexion/extension X-rays, fusion will be defined as less than 2 mm or motion. A cervical spine CT may also be obtained at 24 months on all patients to assess fusion at the discretion of the treating surgeon. All radiographic assessments of fusion will be made by a Washington University staff radiologist, blinded to patient treatment.

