Cellular Analysis: Would consist of bone marrow aspirate and bone marrow aspirate concentration total cell and nucleated cell counts performed on all patients from Group II. Analysis will be performed on 1 cc of aspirate and aspirate concentration harvested at the time of surgery. Additionally, we will measure Hematopoietic stem cell and colony-forming unit fibroblast counts and BMP-2 levels. All cellular analyses will be performed by a hired third party (Immune Disease Institute, Boston, MA) blinded to the study.

Eligibility Inclusion Criteria: Age 18 and 75, able to cooperate in the completion of standardized outcome measures (SF-36 & NDI), willing and able to comply with study protocol.

Eligibility Exclusion Criteria: Pre-existent neurologic disorder or mental disorder that would preclude accurate evaluation (psychiatric disease, Parkinson's disease, Alzheimer's disease), history of previous anterior cervical fusion at the operative site, pregnancy, active malignancy, history of previous posterior cervical decompression.

Data Management and Analysis

Data will be handled in a manner that complies with federal guidelines. Data will be stored on servers maintained by Washington University School of Medicine. This data will be password protected and only approved members of the research team will be granted access. All data management will be performed by a hired third party from Washington University Center for Clinical Studies. Case report forms (CRFs) will be managed using Redcap, a commercially available, web-based data management system. CRFs are completed by the Data entry for the study is web-based. CRFs are completed by the principle investigators and saved to the Redcap server site. All data is readily available for transfer to excel format for statistical analysis and interim evaluations.

Outcome assessments for the primary outcome measure (radiographic fusion) will be provided by staff radiologists of Washington University. The radiologist will be blinded to the clinical treatment received by each patient. Patients will provide completed SF-36 and NDI data at clinical follow-up. This data will be recorded directly by the

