Center for Clinical Studies, while all statistical analysis will be performed by [name] (Biostatistics). All Staff members will randomly audit and verify 10% of the data using graphical, logic and consistency checks applied at several stages of data processing. Data that are manually collected during testing will be entered using forms designed to resemble the CRFs for enhanced accuracy.

Power Analysis: Based on our secondary outcome measures (SF-36 and NDI) preliminary estimates suggest a sample size of 50, per group, will provide greater than 80% power. This estimate was generated by the Department of biostatistics, Washington University to account for variance in the outcome score of SF-36 and NDI. It is anticipated that some patients will achieve a stable asymptomatic non-union, while some patients may fail to achieve any meaningful improvement in SF-36 and NDI scores, despite achieving solid bony fusion. Power estimates were based on a repeated measures analysis of variance (ANOVA) using PowerLib 2.02.

Timeline and Expectations: The proposed study will take 3.5 years to complete (TABLE 1). Patient recruitment will occur in a consecutive randomized fashion as described in the experimental design. Enrollment will occur during the initial 12 months and patients will be followed clinically until 2 years post-operatively. We hypothesize the results from this study will provide supporting evidence that BMAC is equivalent to the current best practice for posterior instrumented fusion in a high risk patient population.

Months	1-12	12-24	24-36	36-42
Recruitment & 1 st Assessment	X			
Surgery Group I & II	X	X		
6 week postoperative assessment	X	X		
3 month postoperative assessment	X	X		
6 month postoperative assessment	X	X		
12 month postoperative assessment		X	X	
24 month postoperative assessment			X	X
Data Analysis/Reporting Results				X

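### The plan gives the pre-operative SF-36/NDI score no covariate role; adjusting for it costs one degree of freedom and narrows the 24-month CI, against the post-operative score alone, once their correlation exceeds about 0.10

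*Combined protocol and SAP*

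**What the plan says.** The Power Analysis section bases the sample size on two secondary outcomes, SF-36 and NDI, and states that "a sample size of 50, per group, will provide greater than 80% power". It then adds: "Power estimates were based on a repeated measures analysis of variance (ANOVA) using PowerLib 2.02". No other model is named in the document. Data Management and Analysis says of the analysis that "all statistical analysis will be performed by" a named biostatistician, and gives no method.

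The pre-operative score will be available. Outcome Measures schedules SF-36, NDI, MDI and mJOA at "pre-operative, 3 months, 6 months, 12 months, and 24 months". Approach places the same four instruments in the pre-operative work-up. The eligibility criteria require patients to be "able to cooperate in the completion of standardized outcome measures (SF-36 & NDI").

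No section says whether the pre-operative score is a covariate, one level of the repeated factor, subtracted to give a change, or unused. The Power Analysis text does mention patients who may not improve meaningfully on these scores. That hints at change but specifies no analysis.

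**The concern.** Repeated measures ANOVA is not a single test. If the pre-operative visit is one of the repeated levels, the arms are compared through the arm-by-time interaction, which is in effect a comparison of change. If only post-operative visits enter, the arms are compared through the main effect of arm. The two differ in precision, and neither uses the pre-operative score as well as a regression on it does.

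This matters because SF-36 and NDI are the only stated basis for the number of patients. Precision on these scores can be gained from data already scheduled. Naming the analysis in advance also removes a choice that would otherwise be open after the data are seen, in a trial that is not blinded.

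**Working it through.** **The plan's own figure.** Power above 80% with 50 per group cannot be reproduced: the plan gives no effect size, SD, correlation or alpha. For orientation only, with an assumed two-sided 5% test of one post-operative score, 50 per group gives 80% power at (1.960 + 0.842) × √(2/50) = 0.56 SD.

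**Inputs.** From the documents: 50 per group, so N = 100, and scores before surgery and at 24 months. Assumed: equal SDs before and after surgery, correlation r between the pre-operative and 24-month scores, no missing data.

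**Formulas.** Variance per patient in SD² units:

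- post-operative score alone: 1
- change from baseline: 2(1 − r)
- adjusted: (1 − r²) × 97/96, where 97/96 = 1 + 1/96 is the expected cost of estimating the slope with 100 patients

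Half-width = t × √(2 × variance / 50) = t × 0.2 × √variance. Here t = 1.9845 (98 df) for the first two and 1.9847 (97 df) for the adjusted analysis.

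**Worked case, r = 0.5.** Score alone: 1.9845 × 0.2 × 1 = 0.397. Change: the variance is 2 × 0.5 = 1, so also 0.397. Adjusted: 0.75 × 97/96 = 0.758, square root 0.871, and 1.9847 × 0.2 × 0.871 = 0.346.

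**24-month 95% CI half-width, SD units:**

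| r | score alone | change | adjusted |
|---|---|---|---|
| 0 | 0.397 | 0.561 | 0.399 |
| 0.1 | 0.397 | 0.533 | 0.397 |
| 0.3 | 0.397 | 0.470 | 0.381 |
| 0.5 | 0.397 | 0.397 | 0.346 |
| 0.7 | 0.397 | 0.307 | 0.285 |

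At r = 0.3/0.5/0.7 the adjusted interval is about 4%/13%/28% narrower than score alone and 19%/13%/7% narrower than change.

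**Break-even against score alone.** Setting (1 − r²) × 97/96 = 1 gives r = √(1/97) = 0.102, or 0.103 once the t quantiles are included. At r = 0 the width ratio is √(97/96) × 1.9847/1.9845 = 1.005. Simulation (40,000 trials per setting) gave width ratios of 1.0052 at r = 0, 1.0002 at 0.10, 0.9589 at 0.3 and 0.8709 at 0.5. With fewer patients analysed, break-even rises to 0.109 (N = 90) and 0.116 (N = 80).

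**Break-even against change.** With equal SDs, change has the smaller variance only when 2(1 − r) < (1 − r)(1 + r) × 97/96, that is when r > 95/97 = 0.979. If the pre-operative SD is s times the post-operative SD, the variance of change is 1 + s² − 2rs = (1 − r²) + (r − s)². It is therefore never below 1 − r², and the adjusted interval can be at most about 0.5% wider. At s = 0.8 this happens for r of about 0.73 to 0.85.

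**What the choice can mean for power.** For an assumed 0.5 SD difference at 24 months, two-sided 5%, at r = 0.3/0.5/0.7: change 55%/70%/89%, score alone 70%, adjusted 73%/81%/93%.

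**Form of the model.** The table is for a slope fitted at 24 months. A mixed model with one slope shared by all visits is not equivalent. Suppose, for illustration, baseline correlations of 0.6/0.5/0.35/0.2 at 3/6/12/24 months, inter-visit correlation 0.7 and equal SDs. With an unstructured covariance the shared slope is about 0.595. The 24-month variance is then 1 + 0.595² − 2 × 0.595 × 0.2 = 1.116, against 1.000 for score alone and 1 − 0.2² = 0.960 with a visit-specific slope (slope-estimation cost left out). Since √1.116 = 1.056, the shared-slope interval is about 5.6% wider than no adjustment.

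**The case against.** The strongest reply is that the gain cannot be sized. The documents give no correlation or SD, these outcomes are secondary, and under randomisation both change and covariate adjustment estimate the same arm difference, so the choice is one of precision and not of validity. All of that stands. It limits the weight of the point without removing it: the loss is bounded at about 0.5% of CI width, while the gain at moderate correlation is several times larger.

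A second reply is that the 0.10 threshold is narrower than it looks. It does hold only against the post-operative score alone, at one visit, with about 100 analysed, and it concerns expected width. In a single trial with r just above 0.10 the adjusted interval can still come out slightly wider. A reader might infer that any baseline adjustment narrows the interval. The shared-slope illustration shows otherwise, which is why the form of the model is part of the fix.

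A reader might also take the expectation that "BMAC is equivalent to the current best practice for posterior instrumented fusion" to mean that the questionnaire scores are to be tested for equivalence. The hypothesis concerns rates of bony fusion, and neither statement mentions the scores. Leaving difference versus equivalence unstated for them is missing detail, not a contradiction.

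**Conclusion.** The point holds as a low-cost gain in precision on the scores that set the sample size. Under equal SDs, no missing data and 50 per group, the adjusted 24-month half-width is 0.381/0.346/0.285 SD at r = 0.3/0.5/0.7, the smallest of the three options at each. With unequal SDs, change can be better by at most about 0.5%, over a limited range of r.

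Two stronger readings are not supported. One is that the trial is underpowered or that the figure above 80% is wrong: the power figures in the working depend on an assumed 0.5 SD difference, and without the plan's own inputs its claim can be neither confirmed nor refuted. The other is that this repairs the primary analysis: it does not affect the fusion comparison and supplies no power basis for it.

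**What to change.** State that post-operative SF-36, NDI, MDI and mJOA are compared between arms with the pre-operative score as a covariate, in one of two forms:

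- ANCOVA at one visit named in advance, such as 24 months; or
- a mixed model with arm, visit, arm-by-visit, pre-operative score and pre-operative score-by-visit, with the contrast at that named visit.

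Report that contrast with its 95% CI.

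The cost is a few sentences of SAP wording, standard software and one degree of freedom per covariate slope. No new data, visits or patients are needed.

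While editing, it would help to give the inputs behind the SF-36/NDI power, to say whether these scores are compared for difference or equivalence, and to settle whether the 6-week questionnaires implied by Approach belong to the schedule in Outcome Measures. Those are clarifications, and the point does not depend on them.
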